## 7. Existing EMS Airway Practices

Historically, US paramedics have favored ETI over SGA for airway management of adult OHCA. However, a shift in practice occurred in the US approximately 5 years ago, with multiple US EMS agencies switching to SGA as the primary device in OHCA resuscitation. Several ROC EMS agencies (including those affiliated with the Dallas, Pittsburgh, and Portland centers) currently utilize SGA as the primary airway management device in patients with OHCA. (Table 2)

We have verified in extensive discussions with the ROC EMS Operations committee that paramedics are willing to randomize OHCA patients to ETI or LT.

[figure not shown]
Supraglottic Airway Used by EMS Agency	
King Laryngeal Tube	20
Combitube	0
Laryngeal Mask Airway	0
i-Gel	0
Supraglottic Airway Used by	
Primary Airway Used in Cardiac Arrest	
Endotracheal Intubation	20
Supraglottic Airway (paramedic discretion)	0
Supraglottic Airway (paramedic protocol)	0
Other	0

**Table 2 - Airway management practices of 33 US EMS Agencies in the Resuscitation Outcomes Consortium**

## 8. Overview of Trial Design

This trial will use a cluster randomized controlled design with periodic crossover. Responding EMS personnel will perform advanced airway management using either primary ETI (control) or primary LT insertion (intervention). The trial will be designed to detect the superiority of either primary ETI or primary LT airway management over the other intervention arm.

**Figure 5 - Overview of Trial Protocol**  
ETI = Endotracheal Intubation; SGA = Supraglottic Airway  
BVM = Bag-Valve-Mask Ventilation

## 9. Inclusion Criteria

This trial will include subjects meeting all of the following conditions:

- Out-of-hospital cardiac arrest (OHCA);
- Adult (age ≥18 years or per local interpretation);
- Non-traumatic etiology;
- Initiation of ventilator support (e.g. Bag-valve-mask device or non-rebreather mask).

The trial will include EMS-witnessed arrests. The trial will include individuals experiencing recurrent OHCA during the same care episode.

If a patient receives bag-valve-mask ventilation but not ETI or SGA, the patient will be included in the study per intention-to-treat principles, regardless of whether the patient regains consciousness or remains comatose. If allowed by local protocol, EMS personnel may use a non-rebreather (NRB) mask instead of BVM ventilation; these patients will similarly be included in the study per intention-to-treat principles.

## 10. Exclusion Criteria

This study will exclude the following subjects:

### ***Protected Populations***

- Known pregnant women;
- Known prisoners;

### ***Trauma***

- c) Major facial trauma (visible major deformity, copious oral bleeding, etc);
- d) Major bleeding or exsanguination (e.g., major upper or lower GI bleed, visceral perforation, major uncontrolled bleeding from laceration or injury);

***Pre-Existing Conditions or Prior Treatment***

- e) Patient receiving initial care by a non-PART participating EMS agency capable of performing ETI, LT or other advanced airway management.
- f) Patients with ET tube, LT or other advanced airway device inserted prior to participating EMS agency arrival (e.g., inserted by healthcare facility personnel);
- g) Patients with a pre-existing tracheostomy;
- h) Obvious asphyxial cardiac arrest (e.g., choking, foreign body aspiration, angioedema, epiglottitis, trauma to mouth and face, etc.);
- i) Patients with a left ventricular assist device (LVAD) or total artificial heart (TAH);
- j) Patients with pre-existing written “do-not-attempt-resuscitation” (DNAR) orders;
- k) Inter-facility transports;

***Other Exclusions***

- l) Patients with a “do not enroll” bracelet.

[figure not shown]
**11. Trial Setting**

EMS agencies associated with US Regional Coordinating Centers of the Resuscitation Outcomes Consortium will be selected for participation in this trial. (Figure 6) Conditions for selection include:

- a) US EMS agency;
- b) Affiliation with US ROC Regional Coordinating Centers;
- c) Use of the King LT as the primary SGA;

EMS agencies that do not utilize King LT SGA will be excluded from the trial.

Per the requirements of the NIH/NHLBI award supporting this clinical trial (RFA-HL-14-019, <http://grants.nih.gov/grants/guide/rfa-files/RFA-HL-14-019.html>).

**Figure 6**  
**The Resuscitation Outcomes Consortium**  
Only select US sites (Alabama, Dallas, Milwaukee, Oregon, Pittsburgh and San Diego) will participate in the trial.

[14-019.html](#)), which do not allow foreign components, only US EMS agencies will participate in the trial.

Candidate EMS agencies will need to meet prequalification criteria to enter the enrollment phase of the trial. (Appendix 3)

## 12. Interventions

### 12.1 EMS Personnel Training Levels

The interventions in this trial may involve coordination between advanced- and basic-level EMS personnel.

- Advanced-level EMS personnel (Advanced Life Support, ALS, paramedic, advanced care paramedic) perform advanced-level interventions, including intravenous drug administration, manual defibrillation, and advanced airway management interventions (ETI and SGA).
- Basic-level EMS personnel (Basic Life Support, BLS, Emergency Medical Technician, EMT) perform basic measures such as CPR and automated defibrillation. Bag-valve-mask ventilation is their primary airway management intervention, although select EMS agencies may perform SGA (LT) insertion. In general, basic-level EMS personnel in the US do not perform ETI.

[figure not shown]
EMS organization and response to OHCA vary across ROC. In some EMS agencies, all responding personnel are trained at the advanced level. In other agencies, OHCA care is tiered, with both basic-level and advanced-level EMS personnel responding to OHCA. Select BLS EMS personnel among ROC EMS agencies perform SGA insertion (Table 2). The trial design will try to accommodate all configurations of EMS response.

### 12.2 Primary Endotracheal Intubation (Control Arm)

In this traditional model of OHCA airway management, advanced-level EMS personnel will use ETI as the primary (initial) airway management intervention. If the EMS agency is assigned to this arm, basic-level EMS personnel will use bag-valve-mask ventilation only even if they would normally use an LT.

#### 12.2.1 ETI Device and Technique

ETI involves placement of a flexible plastic breathing tube between the vocal cords and into the trachea. The customary approach to ETI is through the patient's mouth (orotracheal intubation). The operator inserts a metal lighted blade (laryngoscope) into the patient's mouth to displace the

**Figure 7 – Example of Endotracheal Tube**  
(from [http://commons.wikimedia.org/wiki/Image:Endotracheal\\_tube\\_inserted.png](http://commons.wikimedia.org/wiki/Image:Endotracheal_tube_inserted.png))

tongue and expose the vocal cords. The operator then places the ET tube directly through the vocal cords. (Figure 7)

### 12.2.2 ETI Techniques Permitted in the Trial

Conventional orotracheal intubation is the preferred approach for the primary/initial intubation attempt. Ororacheal ETI is the most common approach in OHCA. EMS personnel may use video laryngoscopy for the primary/initial intubation attempt.

Alternate approaches to ETI (for example, nasotracheal intubation, digital intubation) are less common in OHCA and will not be allowed for the initial intubation effort.

If the EMS agency is assigned to the primary ETI arm, and an alternate ETI technique is used for the primary/initial intubation attempt, the case will be excluded from the study.

If the EMS agency is assigned to the primary ETI arm, and if initial orotracheal ETI attempts are unsuccessful, the EMS agency may use alternate ETI techniques in a “rescue” capacity.

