### Outcomes:

The primary outcome will be:

- 1) **72-hour hospital survival**, defined as patient status (alive/dead) at 72 hours after the initial onset of cardiac arrest.

Secondary outcomes will include:

- 1) **Return of Spontaneous Circulation (ROSC)**, defined as the presence of palpable pulses upon ED arrival.
- 2) **Airway Management Clinical Course**, including sequence of ETI/LT insertion, ETI/LT insertion success and time, number of ETI/LT insertion attempts, and airway conversion (change of LT-to-ETI, or ETI-to-LT) in the receiving Emergency Department.
- 3) **Adverse Events**, including initially unrecognized airway misplacement (including endotracheal tube misplacement), inadequate ventilation requiring airway exchange, vomiting, oropharyngeal, hypopharyngeal or gastrointestinal trauma, and pneumothorax.
- 4) **Hospital Survival**, defined as patient status (alive/dead) at hospital discharge.

- 5) **Hospital Survival with Good Neurologic Function**, defined as Modified Rankin Score  $\leq 3$  upon hospital discharge.

**Analysis:** We will calculate the difference in outcomes divided by the estimated “robust” standard error based on the Huber-White sandwich estimator in order to account for within cluster correlation and variability, which might depart from the classical assumptions. To quantify the treatment effect, we will calculate the 95% CI for the difference in event rates. We will perform the analysis on an intention-to-treat (primary analysis) as well as treatment-received bases (secondary analysis).

**Sample Size:** The trial will require 2,612 subjects (1,306 per group) to have 85% power to detect a 4.5% absolute difference in 72-hour survival, given baseline survival of 13.7% and an overall two-sided alpha of 0.05. To allow for subject withdrawal and lost-to-follow-up, the trial will enroll up to 3,000 subjects.

**Regulatory and Ethical Considerations:** The trial will be carried out under federal rules for Exception from Informed Consent (EFIC) outlined by the guidance document “Waiver of Informed Consent Requirements in Certain Emergency Research” (Federal Register, Vol. 61, pp. 51531-51533, November 1, 1996 - <http://www.gpo.gov/fdsys/pkg/FR-1996-10-02/html/96-24968.htm>), OHRP “Basic HHS Policy for Protection of Human Research Subjects” (45 CFR 46.101(i) - <http://www.hhs.gov/ohrp/humansubjects/guidance/45cfr46.html#46.101>), and FDA regulations 21 CFR 50.24.

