### **12.5.2 Unsuccessful Airway Insertion and Rescue Interventions**

An important metric in this study is the rate of unsuccessful ETI or LT insertion and the need for rescue airway interventions. While success rates for OHCA ETI and SGA insertion in OHCA are relatively high (approximately 90%), the time-critical nature of OHCA requires that rescue airway interventions be initiated promptly. Clinical signs of airway insertion or ventilation failure include the inability to place the airway, inability to confirm proper airway device placement, detectable air leak on insufflation resulting in suboptimal chest rise.

In the event that EMS personnel are not able to insert or ventilate through the assigned airway, they may revert to any alternate airway management strategy. For example, if the patient is assigned to ETI but intubation efforts are unsuccessful, EMS personnel may revert to bag-valve-mask ventilation or LT insertion. Conversely, if the patient is assigned to LT but insertion efforts are unsuccessful, EMS personnel may revert to bag-valve-mask ventilation or ETI. In all cases, subjects will be analyzed by their assigned treatment, per intention-to-treat principles.

While select EMS agencies may carry additional SGA other than the LT, during training we will encourage the use of LT as the preferred rescue device in the event of unsuccessful ETI.

Alternate intubation techniques (nasotracheal intubation, digital intubation, etc.) may be used in a rescue capacity in the event of failed initial orotracheal intubation or LT insertion.

Some EMS agencies perform needle jet ventilation or open cricothyroidotomy. This trial does not preclude the use of these techniques in the event of unsuccessful initial airway insertion.

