### 15.2 Intention-to-Treat vs As-Treated

The intention-to-treat comparison will include the two treatment arms: primary-ETI and primary-LT. Where allowed by local protocol, the primary-LT arm will allow for BLS LT insertion.

The as-treated comparison will encompass the initial advanced airway technique received by the subject, whether the airway insertion is successful or unsuccessful. Practically, this will account for situations where randomization is violated; for example, use of the ETI when the patient is randomized to primary-LT, or BLS rescuer use of LT when the patient is assigned to primary-ETI (and hence BLS BVM). In cases where rescuers use only BVM (without resorting to ETI or LT insertion), this will not be considered a protocol violation, and the subject will be retained in the assigned randomization. In cases where rescuers use a different technique as the initial airway intervention (other than ETI or LT), the subject will be excluded from the as-treated analysis.

While this trial focuses on two airway management strategies (primary-ETI and primary-LT), in execution the course of airway management may encompass other airway management endpoints, including BVM ventilation, use of ETI other than orotracheal technique, use of a SG other than LT, or use of an another airway management technique (for example, cricothyroidotomy). Also, airway insertion efforts may prove unsuccessful, necessitating the use of alternate airway techniques. Therefore, a second as-treated comparison will consider the final result of EMS airway management efforts: a) ETI, b) LT, c) BVM, and d) other airway technique.

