**Table 4 - Sample Size Estimates**  
Effect sizes based upon 13.7% baseline 72-hour survival.

in 72-hour survival after OHCA, with an overall significance level (adjusted for interim analyses) of 0.05 and accommodating up to a 5% loss of precision due to cluster randomization (with crossover).

The estimated effect sizes are based upon observations from the ROC PRIMED Trial. In ROC PRIMED, baseline 72-hour survival was 13.7%. There was a 5.0% absolute difference in 72-hour survival between ETI (13.7%) and SGA (8.7%). To account for potential confounders, for this trial we will use a more conservative figure of 4.5% to represent a minimal clinically significant difference. We designed the trial to have 85% power to detect this difference. Therefore, the required minimum sample size is 2,612 subjects (1,306 per group). To allow for subject withdrawal and loss to follow-up, we have budgeted to enroll up to a total of 3,000 subjects.

The participating US ROC sites (Alabama, Dallas, Milwaukee, Pittsburgh, Portland and San Diego) historically treated over 3,000 OHCA requiring advanced airway management in 2013. Therefore, we expect to have adequate capacity to enroll the requisite number of subjects over the anticipated three-year study period.

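### Section 12.2.2 removes ETI-arm cases from the study because of the technique used at the first attempt, so the primary comparison as written is not intention-to-treat

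*Combined protocol and SAP*

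**What the plan says.** Section 12.2.2 does not allow nasotracheal, digital or similar approaches for the first intubation effort, but lets crews use them for rescue afterwards. It then sets the consequence for an agency assigned to primary ETI: if "an alternate ETI technique is used for the primary/initial intubation attempt, the case will be excluded from the study".

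Other parts of the document bear on who is analysed:

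- The Summary (Analysis) and Section 15.3 make intention-to-treat the primary basis and as-treated the secondary one.
- Section 10 lists the exclusion criteria, and a non-orotracheal first attempt is not among them. Section 15.1 describes exclusion only for patients who fail the inclusion criteria or need no ventilatory support; everyone else is enrolled.
- Section 9 keeps patients who receive only bag-valve-mask or non-rebreather support, citing intention-to-treat.
- Section 12.3.2 bars other supraglottic devices in the LT arm but does not say that a case is removed if one is used.
- Section 12.5.2, on failed insertion and rescue, ends: "In all cases, subjects will be analyzed by their assigned treatment, per intention-to-treat principles".
- Section 15.2 says that when the initial technique is something other than ETI or LT, "the subject will be excluded from the as-treated analysis".

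**The concern.** Assignment is made by cluster and period, before the patient is met. A case dropped because of the technique chosen at the first attempt is therefore dropped after assignment, and Section 13.3 confirms that crews know the assignment. The choice of technique may depend on the patient's state: Section 12.5.4 mentions trismus, and Section 15.5 lists airway placement after ROSC as a subgroup. Patient state is also prognostic. Section 15.5 quotes survival of 28.4% for shockable and 6.2% for non-shockable rhythms.

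If such patients leave the ETI arm while similar patients stay in the LT arm, the arms no longer compare like with like on 72-hour survival. A larger sample does not shrink a bias of this kind. There is a practical problem too: one analyst following Section 12.2.2 and another following Section 15.3 would build different primary datasets.

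**Working it through.** **1. The plan's sample size.** The inputs are 85% power ("We designed the trial to have 85% power to detect this difference", Section 16.1), the rate and error level in the Summary ("given baseline survival of 13.7% and an overall two-sided alpha of 0.05"), the effect ("we will use a more conservative figure of 4.5% to represent a minimal clinically significant difference", Section 16.1) and the clustering allowance ("accommodating up to a 5% loss of precision due to cluster randomization (with crossover", Section 16.1), read here as a standard error 1.05 times larger.

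n per arm = (1.960 + 1.036)² × [0.137 × 0.863 + 0.182 × 0.818] / 0.045² × 1.05²
= 8.978 × 0.2671 / 0.002025 × 1.1025 = 1,305.7, so 1,306 per arm and 2,612 in total.

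This matches the plan exactly. No allowance for alternate-technique exclusions enters it.

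**2. Bias from the rule.** Let p = 13.7% be true survival in both arms, f the share of ETI-arm cases removed and s their survival. The LT arm is left intact.

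Observed ETI survival = (p − f·s)/(1 − f), so bias = f(p − s)/(1 − f).

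The documents give neither f nor s; Section 12.2.2 only describes these techniques as less common. I assume f of 1%, 2% and 5%, and s from 0 to 30%. The upper end is just above the 28.4% quoted for shockable rhythms.

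| f (cases of 1,306) | Bias, s = 0 | Bias, s = 13.7% | Bias, s = 30% | Two-sided type I error (s = 0; s = 30%) |
|---|---|---|---|---|
| 1% (13) | +0.138 points | 0 | −0.165 points | 0.051; 0.052 |
| 2% (26) | +0.280 | 0 | −0.333 | 0.054; 0.056 |
| 5% (65) | +0.721 | 0 | −0.858 | 0.079; 0.093 |

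Example: f = 5%, s = 30% gives (0.137 − 0.015)/0.95 = 12.84%, a bias of −0.858 points, and 0.858/4.5 = 19% of the target difference. With s = 0 it is 0.721/4.5 = 16%.

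The type I error uses SE = 1.05 × √[q(1 − q)/(1306(1 − f)) + p(1 − p)/1306], where q is the observed ETI survival, and the 1.96 critical value.

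**3. Power in one unfavourable case.** Suppose LT is truly better (18.2% against 13.7%) and all excluded cases would have died. Observed ETI survival becomes 0.137/(1 − f). With an effective 1306/1.1025 = 1,185 per arm and the pooled-null two-proportion formula, power falls from 84.9% to 82.5% (f = 1%), 79.9% (2%) or 70.2% (5%).

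The error and power figures are fixed-sample normal approximations that ignore the interim boundaries in Section 16.2.

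**4. With the cases kept.** f = 0, so the bias from this rule is 0 and the planned 2,612 is unchanged.

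**The case against.** The best defence is that the affected group should be small. Section 12.2.2 prohibits these techniques first, calls them less common, and expressly permits video laryngoscopy, which narrows the rule. Section 12.5.4 describes most patients as flaccid and trismus as rare. At a 1% share the effect is negligible, and it is zero if excluded cases survive at the average rate. This stands, and it limits the size of the point. It does not justify a one-arm exclusion whose frequency is not capped.

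Four stronger readings are tempting, and the documents do not support them:

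- *Section 12.5.2 flatly contradicts Section 12.2.2.* Its closing sentence ends a paragraph on airways that could not be inserted or ventilated through. It concerns failure and rescue, not a prohibited first technique.
- *Section 15.2 already confines the removal to the as-treated analysis.* Its rule covers initial techniques other than ETI or LT. Nasotracheal and digital intubation are still ETI, and that section mentions non-orotracheal ETI only when introducing the comparison by final airway. Both sections lean towards keeping these cases, but neither squarely addresses them.
- *The bias could approach 2 points.* A 5% share with 50% survival gives −1.91 points, but 50% is far above the 28.4% quoted for shockable rhythms. It would also place about 33 of some 179 expected ETI-arm survivors (18%) in this one group.
- *Cases already dropped can simply be restored.* Nothing says hospital outcomes are collected for them. The first column of the airway-combination table in Section 14.2.2 lists only ETI and LT, with alternate techniques shown only for rescue.

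It is also fair to say that retention of LT-arm breaches is partly inferred. Section 15.2 supports it where ETI is used first; for other supraglottic devices the plan is silent.

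**Conclusion.** The point holds. As written, Section 12.2.2 makes a post-assignment exclusion in the ETI arm with no stated counterpart in the LT arm, so the primary comparison is not the intention-to-treat analysis promised in the Summary and Section 15.3. The firm conflict is with those two places and with the enrolment description in Sections 10 and 15.1.

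The consequence is a possible bias of unknown direction, probably small. It stays within about a third of a point if no more than 2% of ETI-arm cases are removed, and within 0.86 points at 5%. These limits rest on assumed shares and on assumed survival of 0 to 30%, and not on any figure in the plan. The case for correcting it is that it affects who is counted for the primary outcome and can be removed entirely without enrolling more patients.

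**What to change.** Replace the exclusion sentence in Section 12.2.2 with a statement that every eligible patient in a cluster-period assigned to ETI remains in the ETI arm for the primary and secondary intention-to-treat analyses, whatever technique was tried first. Flag the case as a protocol deviation. In Section 15.2, add one explicit as-treated rule for a non-orotracheal first ETI attempt, worded identically for both arms.

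The cost is a few sentences and some data checks. The first technique and the hospital outcomes must be recorded for these cases. For any already dropped, the coordinating center needs to establish whether outcomes were collected, and report the number dropped by arm and period. The sample size does not change. The edit concerns the analysis set only and takes no position on which techniques crews may use.

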## 12.3 Primary Laryngeal Tube Insertion (Intervention Arm)

In this test model of OHCA airway management, advanced-level EMS personnel will use LT as the primary (initial) airway management intervention. Basic-level EMS personnel will use bag-valve-mask ventilation. If trained to use LT, basic-level EMS personnel may perform LT insertion.

### 12.3.1 LT Device and Technique

The LT is a novel airway device that is inserted blindly through the mouth. The device is designed so that the distal end sits in the proximal esophagus. A single port results in inflation of proximal (hypopharyngeal) and distal (esophageal) cuffs. Fenestrations between the cuffs allow insufflated air and oxygen to indirectly enter the tracheal. (Figure 8)

King Systems is the manufacturer and distributor of LT airways in the United States. There are several such models, including reusable (autoclavable) models as well as models with an esophageal port. We expect that EMS agencies will use only the disposable models of the King LT (LT-D and LTS-D).

Use of the LT in adults with OHCA has been described in a range of studies.

[figure not shown]

Figure 8 – Examples of Laryngeal Tube

[http://www.ambuusa.com/usa/products/clinical\\_studies/king\\_lt%E2%84%A2.aspx](http://www.ambuusa.com/usa/products/clinical_studies/king_lt%E2%84%A2.aspx)

<http://theopsdeck.com/MEDKIT%20CONTENTS/PROD%20-%20AWY.King%20LTD.PMI.htm>

